The primary outcome variable for the first objective will be topics and features (derived using the Latent Dirichlet Allocation [LDA] method for clustering language data) as well as a model-based approach of latent class analysis (LCA). We hypothesize: H1: There will be a difference in themes and topics posted by patients with heart disease and for patients without heart disease and use and engagement

phenotypes reflecting quantity, quality, and interaction of posts will be associated with health status, social media perceptions, and patient activation. The second objective outcome variable will be any CHD event. We hypothesize: H2: Adding digital data variables to conventionally-derived predictive models will improve the AUC for forecasting/predicting a CHD related event in a patient. The third objective outcome measure will be health care utilization measured by cost. We hypothesize: H3: Unique digital data variables identified for patients with heart disease and without heart disease will better predict future health care utilization costs for the health system. The fourth objective outcome measure will be the impact of dynamic health events on CV health behaviors. We have the following three hypotheses: H4,1: Digital media data will provide valid measures of health behaviors when compared with traditional sources. H4,2: Variations in digital data about modifiable CV health behaviors will correlate with dynamic health events. H4,3: Modifiable CV health behaviors (smoking, poor diet, and reduced physical activity) will increase more in response to dynamic health events in low income and minority communities.

Secondary outcome variable(s)

Given the correlational nature of this research the distinction between primary and secondary outcome variables is not particularly apparent.

Background

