
screener questions will be the same as the questions already built into our eligibility survey. If the patient is interested, they will receive a link to an eligibility survey to complete either over the phone with a team member or on their own time. The link will be sent via our secure shared Penn medicine email, MPM, or W2H on our HIPAA secure survey platform. If the patient is eligible and still interested, they will be asked to fill out a baseline survey at a time that works best for them. At that time, interested participants will be asked to complete the informed consent HIPAA authorization process at that time. The HIPAA authorization will also include detailed information about the request for permission to collect cost data. For example We are asking permission to collect information on your Medicare and/or insurance coverage and on your cost of care. This information will be collected directly from your insurance and medical record. Information will be collected for up to 5 years. If you agree to participate in this study the following information will be collected: type of health insurance, health insurance provider, health insurance policy, health insurance group number, and the policyholder's name and date of birth will be collected. If we aren't able to obtain your health insurance policy number, we will either call you to obtain your policy number or you can fill out a secure survey through REDcap that will allow you to input your policy number. For in-person enrollment, after the patient signs the informed consent the AA or CDH staff will complete the baseline survey and continue the enrollment process. Patients will complete several surveys on a research laptop (ThinkPad or MacBook air) and/or an iPad (e.g. NHANES: SES [income, education], diet behavior and nutrition, physical activity and physical fitness, smoking, and tobacco use; digital data use [Pew questionnaire]). For patients outside of UPHS, we will ask them to upload screenshots and/or self-report information from their office visit summaries, labs, vital signs, ED and inpatient hospital admission information since we will not have access to their EHR. For in-person enrollment, the survey will be collected on an incognito browser through either <https://donate.centerfordigitalhealth.upenn.edu> or REDcap. Once the survey is completed, the patient will reach a donate data page on the same browser, <https://donate.centerfordigitalhealth.upenn.edu> or be taking to another survey to share their digital data, <https://donate.centerfordigitalhealth.upenn.edu>, on one of the research laptops. For remote enrollment, participants will receive a link via email from our HIPAA secure survey platform to complete the baseline survey either on their own time or over the phone with a study team member. Interested participants will be asked to fill out a brief survey, via Redcap, asking what days and times work best for them to set-up a phone call with one of our team members to go over what is involved in participating in the study. They can either complete the enrollment process on the phone with the team member or on their own time. Subjects who meet case or control criteria, complete the consent process, and opt to share their social media data with the research team, will be instructed on how to share this information by logging into apps for Facebook and Instagram that have been created solely for the purpose of research. They will first be asked to create an account on our secure digital data platform/application (<https://donate.centerfordigitalhealth.upenn.edu>). Once they have confirmed information in the data collection survey, they will be directed to a Facebook application called Penn Image Station that was designed for the purposes of this study. The Penn Image Station application will gather information from their Facebook public profile, status updates, personal description, and likes. The application will not affect their usual use of Facebook nor will it post on their page. Facebook data will be collected prospectively for 60 days. If the participant shares their Instagram posts, they will be directed to an Instagram application called Penn Social Mediome. They will read a brief statement, either agree or disagree with the statement, and then log on to their Instagram account. Their Instagram posts and photos will be extracted by the Penn Social Mediome application and will be collected for 60 days prospectively. If our data collection application is not working, there will be a back-up plan set in place. We will ask participants to share their Instagram usernames so we to pull data manually from their account. If there are technological difficulties with our data collection application, we will reach out to participants at a later time to share their Instagram and Facebook data through the participants unique data sharing url. If there are technical difficulties with our application pulling Facebook data, we will ask participants to manually download a file of their Facebook data from their account. No passwords would be collected by the study team. If the patient has Twitter or Reddit accounts and wish to share that data as well, they will be asked to provide their Twitter handle (username) and/or Reddit handle (username). The participants IP addresses from their devices will be collected. If subjects opt and consent to share Google take-out information with us, they will download a zip file of their google searches and YouTube activity. Google take-out data is only retrospective. They will upload the zip file to the browser <https://donate.centerfordigitalhealth.upenn.edu>. If subjects opt and consent to share step tracking data with our research team and the patient is eligible and has Apple Health, S Health, Garmin, or Fitbit, they will export the data from the specific step tracking platform and the patient will upload this data to <https://donate.centerfordigitalhealth.upenn.edu>. Data collection manual outlines all data extraction procedures [See Appendix]. Data extracted from Facebook will include: age, gender,

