
language, photo, work history, education history, hometown, interests, relationship status, current city, religious or political views, number of friends, items "liked", and number and status updates. Data from Twitter will include: handle, number of followers/following, tweets, geography, time/date, profile. Data extracted from Reddit will include: Reddit posts, comments to posts, your votes "up" or "down" to posts, and the sub-reddits(forums) that youve joined. Data from Instagram will include image posts, time of posting, and image captions. Data extracted from Google takeout includes the search terms, website visited with the URL, YouTube search history, date, and Google fit that includes activities and daily aggregations. If sharing Apple Health, data extracted will include: any data stored or gathered by the Health app and any associated devices, including any Medical ID data, the native iPhone step counter and distance tracker, any data from an Apple Watch, and any data gathered from anythird partydevices that are syncing to Health app, like a smart scale or blood pressure monitor. (<http://osxdaily.com/2019/05/20/export-health-data-from-iphone/>). If sharing Fitbit, data extracted will include: Activity, Exercise, Social, Sleep, Coach, Corporate, Logs, Profile, Direct messages, Female health, Sleep score, Friends, Subscriptions. If sharing Garmin, data extracted will include: steps per month for the past 12 months. If sharing S Health, data extracted will include: Daily step count for 34 days prior to export date(<https://medium.com/@dimshik100/how-to-extract-your-personal-samsung-health-data-514bbe2331f7>). If sharing MapMyFitness, data extracted will include: Date Submitted, Workout Date, Activity Type, Calories Burned, Distance, Workout Time, Average Pace, Max Pace, Average Speed, Max Speed, Average Heart Rate, Steps, Source, Link *we do not use this as it requires user login to view link results*. Patients who donated at least one of the following digital data sources: social media, google takeout zip file, or step tracking data will receive \$50 for survey completion. For in-person enrollment, the entire process will take place during one encounter lasting approximately 15-60 minutes. For remote enrollment, the process can take 15-60 minutes in one session or up to a week or more depending on completion of all enrollment steps. If participants are unable to donate desired digital data sources, we will contact them up to 4 times in a month to download and donate all relevant sources as well as complete the baseline survey if they havent already done so. All patient enrollment status tracking will be documented and saved in either our Penn Medicine secure shared drive, Penn Box (HIPAA compliant feature), or REDcap. From the above cohort we will additionally consent these patients to complete several surveys, if they opt to participate in this additional part of the study. These include: perceptions of health status and perceptions about social media will be assessed as this could impact engagement with a digital intervention. In addition to recontacting the above cohort, we will also identify an additional cohort from iConnect (Penn Medicine research registry), who opt to participate in focus groups that will evaluate perceptions about use and engagement phenotypes, details about individual use of social media platforms, concerns and ways to mitigate concerns about phenotyping, potential uses of phenotypes, opportunities for patient centered design and implementation. Patients will complete a separate informed consent to participate and participation will be anonymous. Interviews will occur via virtual conference call and recorded. After the patient has completed enrollment, we will send them a follow-up summary about the status of the study (ie. how many participants are enrolled and the number of different data sources shared. This application and methodology have been previously used by investigators in this protocol for research within the World Well Being Project at the Positive Psychology Center at the University of Pennsylvania (prior Penn IRB protocols #816091, 813820, 819442, 824493).

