
features with survey data. For example, NHANES survey questions (e.g. Do you now smoke cigarettes?) would be compared with images of cigarette smoking. For Objective 2: We will compare prediction models with and without digital variables. Probability weighted Cox proportional hazard analysis with robust variance estimates will be used to assess the association between each variable from digital media and CHD in univariable and multivariable models. We will use graphical and analytical methods to test the proportional hazards assumption for each analysis. To evaluate the predictive strength of digital data, we will build four predictive machine learning models using a stepwise sequence to select the most parsimonious model using combinations of risk factors. (1. Framingham predictors / American College of Cardiology ASCVD Risk Estimator Plus alone, 2. Framingham predictors / American College of Cardiology ASCVD Risk Estimator Plus + SES, 3. Framingham predictors / American College of Cardiology ASCVD Risk Estimator Plus + digital topics/features, 4. Framingham predictors / American College of Cardiology ASCVD Risk Estimator Plus + digital topics/features+ SES) For Objective 3: We will use Super Learner, the ensemble machine learning approach which allows for the specification of multiple plausible candidate prediction models. Each of the candidate models is applied to a training set and outcomes are predicted using the validation set. A loss function is calculated within each validation set and then averaged across validation sets, which provides the estimated cross-validated risk score for each method. Calibration will be assessed using a calibration plot comparing the predicted probabilities (obtained using fixed regression coefficients of the prediction models) with the observed probabilities. The Super Learner algorithm finds the optimal weighted combination across all of the specified methods. Van der Laan et al. proved the asymptotic efficiency of the Super Learner algorithm and demonstrated that the optimal combination performs at least as well as the best estimators from the candidate models. We will implement Super Learner in R (The R Foundation for Statistical Computing). In this approach generalized estimating equation (GEE) and generalized linear mixed effects models will be explored to account for repeated measures per patient over time. One of the challenges of cost analyses is censoring, since cost may be incomplete and available for some patients and not others. As the dependent variable will be cost, we will be attentive to informative censoring and right skewness, potentially using generalized linear models under a gamma distribution and log link. To account for informative censoring we will use inverse probability of censoring weighting. We will also explore the application of our new nested g-computation approach that allows for informative censoring and time-varying covariates to obtain future cost predictions. Additionally, we will generate summary statistics to describe the cohort and survey responses. We will use the model-based approach of latent class analysis (LCA)- to classify individuals into previously unmeasured subgroups. Variables to include in the LCA will include: demographics, years of platform use, posting: volume, quality, retransmission, and engagement. We will use the Bayesian information criterion to assess goodness of model fit, entropy to assess variations between classes, and the parametric bootstrapped likelihood ratio test to assess if a model with k classes has better performance than k-1 classes. We will then use a regression model to compare with measures of health status, social media perceptions, and readiness/activation for each latent class. Models will be adjusted for demographics.

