## Final Analysis Plan

As digital data exist in multiple formats (e.g. posts, photos, searches, steps) we will analyze each source according to its specific attributes. We will systematically apply robust data-driven approaches to parsing and stratifying data. This step requires significant data pre-processing and annotation as raw digital data is not directly interpretable. This will also occur over multiple iterations over the course of the grant as new terms (e.g., the term "vaping" describes use of e-cigarettes) and digital sources emerge. To automatically extract meaningful variables from the text, we will use both dictionary-based (e.g., counting words from previously constructed word lists, lexica) and data-driven "open vocabulary" methods which automatically generate lexica and identify important words and phrases based on the data itself rather than *a priori* categories. For dictionary analyses, we will use the Consumer Health Vocabulary, an online open source thesaurus of colloquial and technical medical terms and the Unified Medical Language System which contains lists of medical terms and vocabulary to identify disease discussions. We will specifically focus on words and words associated with previously identified predictors of CHD (e.g. demographics, family history, lifestyle, comorbidities, blood pressure) as identified in a systematic review of prediction models for cardiovascular risk by Damen et al. BMJ 2016. We will create classifiers to determine if a given instance of a disease term is referring to the disease or something unrelated (e.g. "If I see a celebrity I will have a heart attack" vs. "I am having chest pain, SOB and had a prior heart attack"). Our prior work has demonstrated that, as one might guess, some CV diseases, like "hypertension", are almost always used in their medical context while others, like "heart attack", are often used colloquially. We will also create classifiers to categorize language by broad grouping such as risk factors, treatment, medication adherence, symptoms, and by more granular categories such as active/sedentary, healthy food/unhealthy food, smoking. We will compare the performance of several machine-learning algorithms (e.g. support vector machines, random forests, and, in cases with adequate data, deep learning) and assess the accuracy of our disease term classifier against hand-annotated data. For multiword phrases we will use approaches for determining the probability that words occur together (e.g., pointwise mutual information PMI). We will also use additional linguistic models to account for more subtle language complexities and nuance such as parts of speech, and disambiguated words. We will use automated computational methods (e.g., deep learning-based object recognition) combined with manual coding to classify features (e.g., healthy or unhealthy food, physical activity, smoking, and drinking) in images. To determine nutritional content of food images, for example, we will use the imagga.com image classification software, combined with analysis of the words used in the text associated with images to recognize

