
summary statistics to describe patient demographics, survey response data, and digital data usage (e.g. frequency of posting, number of social media platforms). Descriptive data will be presented as mean (SD) for continuous variables and frequencies of participants for categorical variables. 5b Extracting topics and features: We will use the Mallet package for implementation of the Latent Dirichlet Allocation (LDA) method for clustering language data of all participants. The LDA probabilistic model assumes that documents (e.g. Facebook status updates) contain a distribution of topics which then contain a distribution of words. Ultimately, words are grouped together by considering the other words they appear with. Descriptive statistics, t-tests (continuous measures) and chi-squared tests (categorical measures) will be used to compare topics and features with survey data. For example, NHANES survey questions (e.g. Do you now smoke cigarettes?) would be compared with images of cigarette smoking. For Objective 2: We will compare prediction models with and without digital variables. Probability weighted Cox proportional hazard analysis with robust variance estimates will be used to assess the association between each variable from digital media and CHD in univariable and multivariable models. We will use graphical and analytical methods to test the proportional hazards assumption for each analysis. To evaluate the predictive strength of digital data, we will build four predictive machine learning models using a stepwise sequence to select the most parsimonious model using combinations of risk factors. (1. Framingham predictors / American College of Cardiology ASCVD Risk Estimator Plus alone, 2. Framingham predictors / American College of Cardiology ASCVD Risk Estimator Plus + SES, 3. Framingham predictors / American College of Cardiology ASCVD Risk Estimator Plus + digital topics/ features, 4. Framingham predictors / American College of Cardiology ASCVD Risk Estimator Plus + digital topics/features+ SES) For Objective 3: We will use Super Learner, the ensemble machine learning approach which allows for the specification of multiple plausible candidate prediction models. Each of the candidate models is applied to a training set and outcomes are predicted using the validation set. A loss function is calculated within each validation set and then averaged across validation sets, which provides the estimated cross-validated risk score for each method. Calibration will be assessed using a calibration plot comparing the predicted probabilities (obtained using fixed regression coefficients of the prediction models) with the observed probabilities. The Super Learner algorithm finds the optimal weighted combination across all of the specified methods. Van der Laan et al. proved the asymptotic efficiency of the Super Learner algorithm and demonstrated that the optimal combination performs at least as well as the best estimators from the candidate models. We will implement Super Learner in R (The R Foundation for Statistical Computing). In this approach generalized estimating equation (GEE) and generalized linear mixed effects models will be explored to account for repeated measures per patient over time. One of the challenges of cost analyses is censoring, since cost may be incomplete and available for

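### Objective 2 lets digital features restate the CHD diagnosis or its treatment, with no index-date cut-off or exclusion rule, so an AUC gain under H2 could not be read as forecasting an event

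*Protocol*

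**What the plan says.** **Hypothesis and models.** H2 (Protocol, Primary outcome variable(s)) reads: "Adding digital data variables to conventionally-derived predictive models will improve the AUC for forecasting/predicting a CHD related event in a patient". The Objective 2 text, the same in the Protocol's Analysis Plan and the SAP's Final Analysis Plan, lists four models. Model 1 is "Framingham predictors / American College of Cardiology ASCVD Risk Estimator Plus alone". The next two are "2. Framingham predictors / American College of Cardiology ASCVD Risk Estimator Plus + SES" and "3. Framingham predictors / American College of Cardiology ASCVD Risk Estimator Plus + digital topics/features". Model 4 adds both SES and the digital block. The variables in the digital block are not listed, and no pair of models is named as the H2 test.

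**Features.** The SAP plans classifiers that separate genuine disease mentions from colloquial ones; its example of a genuine mention describes symptoms and an earlier heart attack. Further classifiers "categorize language by broad grouping such as risk factors, treatment, medication adherence, symptoms". Text, image and sensor features are then to be combined in one predictive model.

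**Cohort and timing.** Under Overall objectives, Objective 2 uses a retrospective cohort with and without heart disease. Design takes patients with CVD in the last 5 years, and the exclusion criteria remove older heart attack, stroke or CAD. Under the inclusion criteria, Facebook and Instagram data are historical plus 60 days prospective.

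**Other fields collected.** Apple Health extraction covers "any data stored or gathered by the Health app and any associated devices, including any Medical ID data", and synced devices such as a scale or blood-pressure monitor. Facebook extraction includes "language, photo, work history, education history, hometown, interests, relationship status, current city".

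**The concern.** A case enters this cohort because the disease has already occurred. The digital record then includes whatever was written between the event and enrolment, and in the 60 days after. For cases diagnosed before enrolment, every prospective post follows the diagnosis. Features built to detect true disease mentions and treatment talk will pick up people describing the illness that made them cases. Such a feature separates cases from controls well and predicts nothing.

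The only difference between model 3 and model 1, or between model 4 and model 2, is a block whose content is undefined. If that block contains disclosures of the outcome, H2 can be declared supported with no forecasting value, and the analysis as planned would not reveal it.

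**Working it through.** **1. Is there a figure to reproduce?** No. The Protocol gives a target of 1000 participants, but no baseline AUC, AUC difference, alpha, power, event count or case/control split. The numbers below are illustrations with assumed inputs.

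**2. Tracing items from collection to model.**

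| Item | Collected | Built into features | Explicitly in models 3 or 4 | Excluded or cut off at the event |
|---|---|---|---|---|
| Genuine disease mentions | yes | yes (classifier) | through the digital block | no |
| Treatment, adherence, symptom language | yes | yes (classifier) | through the digital block | no |
| Medical ID | yes | not stated | no | no |
| Synced blood-pressure and scale readings | yes | not stated; sensor data are to be pooled | no | no |
| Facebook education and work fields | yes | not stated | no | no |

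The first two rows carry the point. The other three are collected and not excluded, and no more than that.

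**3. Size of the gain from a pure disclosure marker.** Assume a comparator AUC *A*, a binary marker in a fraction *p* of cases and *f* of controls, independent of the comparator score given case status, with no other information. If the marker outranks the score, the combined AUC is

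p(1−f) + [pf + (1−p)(1−f)]·A.

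With A = 0.75 and f = 0.01:
- p = 10%: 0.099 + 0.892 × 0.75 = 0.768, gain +0.018
- p = 20%: 0.198 + 0.794 × 0.75 = 0.7935, gain about +0.043
- p = 30%: 0.297 + 0.696 × 0.75 = 0.819, gain +0.069

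At f = 0.05 the marker is too common in controls to outrank the score, so it should be weighted by its likelihood ratio. With a binormal score, z = Φ⁻¹(A) and D = ln(p/f) − ln[(1−p)/(1−f)], the combined AUC is

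[pf + (1−p)(1−f)]·A + p(1−f)·Φ((2z²+D)/2z) + (1−p)f·Φ((2z²−D)/2z).

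With A = 0.75 (z = 0.6745):
- p = 10%, D = 0.747: 0.645 + 0.095 × 0.890 + 0.045 × 0.548 = 0.754, gain +0.004
- p = 20%, D = 1.558: 0.5775 + 0.19 × 0.966 + 0.04 × 0.315 = 0.774, gain +0.024
- p = 30%, D = 2.097: 0.51 + 0.285 × 0.987 + 0.035 × 0.189 = 0.798, gain +0.048

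Simulation gives the same gains for both values of f. Over A = 0.70 to 0.80, p = 10% to 30% and f = 1% or 5%, the gain runs from +0.003 (A = 0.80, p = 10%, f = 5%) to about +0.084 (A = 0.70, p = 30%, f = 1%: 0.297 + 0.696 × 0.70 = 0.784).

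**4. Would such a gain be declared?** Assume 500 cases and 500 controls, A = 0.75, two-sided 0.05 and a known marker weight. Simulated power is about 0.92 for 10% versus 1%, 0.93 for 20% versus 5%, and above 0.99 for 20% versus 1%.

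**5. Repeat measurements.** An exact copy of a comparator variable adds 0.000. A second reading with the same reliability r, with error variance v = (1−r)/r, gives AUC Φ(z·√[(1+v)/(1+v/2)]). At A = 0.75 the gain is about +0.005 (r = 0.9), +0.018 (r = 0.7) or +0.032 (r = 0.5). This treats the re-measured factor as the whole comparator, so blood pressure or weight alone would add less.

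**The case against.** **H2 is about digital data variables, not digital behaviour.** This stands. The abstract counts a better characterization of existing risk factors among the hopes for digital data, so a gain from home blood-pressure readings would satisfy H2 as worded. A reader might infer that H2 is invalid unless the gain comes from behaviour; the documents do not support that. But H2 also speaks of forecasting an event, and a post announcing the event does not forecast it.

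**Collection is not model entry.** This stands too. A reader might infer that Medical ID, device readings and profile fields are predictors in models 3 and 4. The documents show only that they are extracted, and eligibility describes device sharing as step data. With the digital block undefined and sensors to be pooled, entry is possible but not established.

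**Age, gender and SES.** A reader might infer that Facebook age and gender inflate the gain, or that SES is credited to digital data. Exact copies of comparator variables add nothing. Models 2 and 4 carry SES on both sides, and no text makes model 3 versus model 1 the test. What remains is that no contrast is named.

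**The comparator lacks matching diagnosis information.** This cannot be checked, because the documents do not list the Framingham/ASCVD inputs.

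**A date cut-off would remove most disclosures.** For dated posts this is largely right, and the exclusion of disease older than 5 years helps. But the plan has no cut-off. The Cox analysis does not supply one, since no time origin or covariate date is given for it. A cut-off also cannot act on undated fields.

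**Conclusion.** The concern holds for disclosed diagnosis and treatment. The plan builds these features, pools them, and applies them to a retrospective cohort with post-diagnosis data and no cut-off or exclusion. A positive H2 result could therefore not be interpreted as prediction. For Medical ID, device readings and Facebook education and work fields, it holds only as an omission: they are collected and nothing keeps them out.

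The size depends on unknown disclosure rates. At an assumed comparator AUC of 0.75 and a marker in 10% to 30% of cases, the spurious gain is +0.018 to +0.069 with the marker in 1% of controls, and +0.004 to +0.048 with 5%. The control rate matters greatly: at 10% of cases and 5% of controls the effect is almost nil. The result also assumes that the marker is independent of the conventional score within cases and within controls.

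**What to change.** In the Objective 2 text of the SAP and the Protocol's Analysis Plan:

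1. For the H2 test, use only digital data dated before the index event, with a matched reference date for controls. Before topic modelling, remove posts and searches that state a CHD or stroke diagnosis or its treatment. The filter has to act on posts because topic and open-vocabulary features mix disease words with others. Adherence language in general need not be dropped, since adherence is itself a health behaviour.
2. List the variables in the digital block. Leave undated snapshot fields (Medical ID, profile education and work) and device blood-pressure and weight readings out of the H2 set.
3. Name model 4 versus model 2 as the H2 contrast.
4. Report the unrestricted digital set as a secondary analysis. The difference between the two gains shows how much rests on disclosure and the other excluded data.

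**Cost.** No new data collection is needed. The planned disease-term and treatment classifiers give a start on the filter, but it needs extra work and some hand checking. There will be less usable data per participant, and probably a smaller AUC gain.
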